## **8.10 Breaking the Blind for Individual Subjects**

While this is a double-blind study, the blind may be broken if a subject's health or safety is at risk and knowledge of the study arm may be beneficial to the medical management of the subject. In an event of unblinding, Emergent must be notified.

If the Investigator determines that knowledge of a subject's treatment assignment is urgently needed in order to guide treatment or ensure the subject's safety, the Investigator may perform emergency unblinding via RTSM system. The Investigator may not delegate this responsibility. The Investigator must attempt to notify Emergent's Medical Monitor prior to unblinding and must notify Emergent's study MM within 24 hours after unblinding at the latest.

If a subject's study treatment assignment is unblinded for safety reasons, or if a subject becomes accidentally unblinded for any reason, the subject will be requested to remain in the study for safety follow-up. Documentation of breaking the blind must be entered in the study subjects' source documents with the following information recorded: (1) date and time the blind was broken; (2) the rationale behind the unblinding decision/occurrence; (3) the names of the personnel involved; and (4) date of contact with Emergent's study MM.

## **8.11 Study Safety-Pause Rule**

Study enrollment and administration of study treatments may be temporarily paused by the SMC for safety review, if any of the following occur after study treatment administration and during the study's follow-up period:

- One or more SAE(s).
- Three or more of the same AEs classified as grade 3 severity.
- Five or more of the same AEs classified as grade 2 severity.

These events will be reviewed by the SMC and a recommendation will be made. The procedures will be outlined in the SMC Charter.

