Study Arm	No. of Subjects	Dosing Schedule – Day 1														
1	8	COVID-HIGIV dosage 1*														
2	8	COVID-HIGIV dosage 2**														
3	8	COVID-HIGIV dosage 3***														
4	4	Placebo (saline)														

	
unit once all assessments at 24 hours post-dosing timepoint (i.e., Day 2) are completed.
 
The SMC will perform overall ongoing review of safety data during the study. Study enrollment and administration of study treatments may be temporarily paused by the SMC for safety review if any of the following occur after study product administration and during the study's follow-up period:
 
 
• One or more serious adverse event(s) [SAE(s)].
 
• Three or more of the same adverse events (AEs) classified as grade 3 severity.
 
• Five or more of the same AEs classified as grade 2 severity.
 
 
Note: refer to Section 8.2 for AE severity grading.
 
Placebo recipients may be unblinded upon request after all subjects have completed Day 29 to allow them to follow current COVID-19 vaccination guidelines.
 
Subjects will be followed up for safety and PK up to 84 days post-administration of a single dose.
 
If any subjects become positive for SARS-CoV-2 during the study follow-up period, they will be assessed using modified WHO ordinal score (see Appendix I – Modified WHO Ordinal Scale) until they complete their last follow-up visit (via telemedicine).

Inclusion Criteria	
The following criteria will be used for inclusion into the study:
 
 
1. Able and willing to provide written informed consent (voluntarily signed by the subject) prior to performing study procedures.
 
2. Females and males 18-60 years of age, inclusive.
 
3. Have a body mass index (BMI) less than or equal to 35.0 kg/m^2.
 
4. Women who are either: 
 
A) Not of childbearing potential: either surgically sterile (at least six weeks post bilateral tubal ligation, bilateral oophorectomy or hysterectomy); or post-menopausal (defined as <math>\geq</math>50 years of age with a history of <math>\geq</math>12 months without menses prior to randomization in the absence of other pathologic or physiologic causes, following cessation of exogenous sex-hormonal treatment); OR
 
 
 

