### **5.1.6 Administration**

Ensure the recipient is adequately hydrated prior to initiation of IV infusion.

Administer COVID-HIGIV by IV infusion through a dedicated IV line using a constant infusion pump (e.g., IVAC® pump or equivalent).

Administer COVID-HIGIV within 24 hours of preparation into an IV infusion bag.

Set the starting infusion rate at 1.0 mL/min for the first 30 minutes. If the infusion is well tolerated, double the infusion rate to 2.0 mL/min for the next 30 minutes, and if tolerated, double the rate to 4.0 mL/min (maximum rate) which should be used for the remainder of the infusion.

For example, at the recommended infusion rates above (with no interruptions or reduction in the infusion rates), dose volume of 400 mL should be infused within 2.5 hours.

Monitor subjects closely during infusion and within 24 hours after completion of COVID-HIGIV infusion.

If AEs occur during the IV infusion, such as grade 1 (mild) events of flushing, headache, chills, fatigue, nausea, slight changes in pulse rate or blood pressure, slow the rate of infusion or temporarily stop the infusion until symptoms subside (at discretion of the investigator). Once the AEs resolve, resume the infusion at a rate that is comfortable to the subject (e.g., start the infusion at half of the last tolerated infusion rate and increase gradually). If the recipient experiences grade 2 (moderate) or higher AEs such as chest pain, difficulty breathing, vomiting, arthralgia, or severe headache, unresponsive to slowing the infusion rate or stopping of the infusion, do not resume the infusion.

Stop the infusion if serious AEs develop (e.g., anaphylaxis, severe hypersensitivity reactions) and administer appropriate medical management. Do not restart the infusion.

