## APPENDIX IV – GRADING OF VITAL SIGNS

Use the following criteria to grade vital signs:

Grading Scale*	Grade 1 (mild)	Grade 2 (moderate)	Grade 3 (severe)	Grade 4 (potentially life-threatening)
Temperature (C°) (F°)	38.0-38.4 100.4-101.1	38.5-38.9 101.2-102.0	39.0-40.0 102.1-104.0	>40.0 >104
Tachycardia (beats/min)	101-115	116-130	>130	ER visit or hospitalization for arrhythmia
Bradycardia (beats/min)	50-54	45-49	<45	ER visit or hospitalization for arrhythmia
Hypertension systolic (mmHg)	141-150	151-155	>155	ER visit or hospitalization for malignant hypertension
Hypertension diastolic (mmHg)	91-95	96-100	>100	ER visit or hospitalization for malignant hypertension
Hypotension systolic (mmHg)	85-89	80-84	<80	ER visit or hospitalization for hypotensive shock
Respiratory Rate (breaths/min)	17-20	21-25	>25	Intubation
SPO 2 (%)	92 - <95	90 - <92	85 - <90	<85 or ER visit or hospitalization for hypoxia

\* Taken from Toxicity Grading Scale for Healthy Adult and Adolescent Volunteers Enrolled in Preventive Vaccine Clinical Trials {CBER, 2007}, except SPO2.

Document Approvals  
Approved Date: 21 Apr 2021

Approval Task Verdict: Approve	Director, Clinical Development
	21-Apr-2021 15:23:11 GMT+0000

Approval Task Verdict: Approve	
	21-Apr-2021 15:24:22 GMT+0000

Approval Task Verdict: Approve	tor, Clinical Research
	21-Apr-2021 15:37:29 GMT+0000

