### 9.2.1 Overall Summary of AEs

The following list of AEs summaries will be provided by SOC and PT in tabulate format. The events will be sorted in descending frequency of subjects in the "Total" column for SOC, then PT, unless otherwise specified.

- All AEs
- All AEs occur within 72 hours post-dosing (from the start of infusion to 72 hours post the end of infusion)
- All AEs by maximum severity
- AEs related to study treatment (COVID-HIGIV or placebo)
- AEs of Grade 3 and higher severity
- AEs of Grade 3 and higher severity and related to study treatment
- AEs by analysis group sorted by PT in descending frequency among all COVID-HIGIV treated subjects AE Severity

The Investigator is responsible for the assessment of the severity of an AE using the following criteria:

- Mild (Grade 1): awareness of a sign or symptom but subject can tolerate.
- Moderate (Grade 2): discomfort enough to cause interference with normal daily activity.
- Severe (Grade 3): resulting in an inability to do work or do usual daily activity.

[COVID-HIGIV]  
[EBS-CVH-003]

- Potentially Life-Threatening (Grade 4): emergency room visit or hospitalization.
- Death (Grade 5)

Subjects having the same AE more than once will be counted once for each PT and once within each SOC at the maximum severity. If the severity is missing for one or more of the occurrences, the maximum severity of the remaining occurrences will be used.

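### The pause rule counts grade 2 and grade 3 occurrences of the same AE separately, so a more severe mix can fail a criterion that a milder one meets

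*Protocol*

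**What the plan says.** Protocol 8.11 lets the Study Monitoring Committee (SMC) temporarily pause enrolment and dosing for a safety review when any one of three criteria is met: at least one SAE, "Three or more of the same AEs classified as grade 3 severity", or "Five or more of the same AEs classified as grade 2 severity". It then commits that "These events will be reviewed by the SMC and a recommendation will be made" and leaves the procedures to the SMC Charter, which is not among the documents. The synopsis has the same list ("Three or more of the same adverse events (AEs) classified as grade 3 severity"), and so does SAP 2.2.

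None of the three places pools grades or mentions grade 4. Elsewhere the documents use cumulative wording. The infusion instructions in Protocol 5.1.6 say "If the recipient experiences grade 2 (moderate) or higher AEs", and SAP 9.2.1 plans a table of "AEs of Grade 3 and higher severity".

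**The concern.** The thresholds fall as the category becomes more serious (five, three, one), which is sensible. The difficulty is how occurrences of different grades combine. A pause trigger should never switch off because one of the counted events turned out worse. With separate counts, it can: upgrading one of five grade 2 events to grade 3 removes it from the grade 2 count without bringing the grade 3 count to three.

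The criteria define which events carry the commitment to an SMC review and recommendation in 8.11. A cluster of one AE can fall outside that commitment because some of its members were more severe. This is a healthy-volunteer study in which all three dose levels, including 400 mg/kg, are randomized from the first seven subjects, so the listed triggers should be right as written.

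**Working it through.** The plan gives no operating characteristics for the rule, so there is no stated figure to reproduce.

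**Step 1: which patterns fall through.** For one AE term with no SAE, let *a* be the number of grade 2 occurrences and *b* the number of grade 3.

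- As written, a criterion is met if *a* ≥ 5 or *b* ≥ 3. None is met when *a* ≤ 4 and *b* ≤ 2.
- With *or higher*, a criterion is met if *a* + *b* ≥ 5 or *b* ≥ 3.
- Patterns with *a* + *b* ≥ 5 that meet nothing as written: (4,1), (3,2) and (4,2).

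The largest pattern meeting nothing is (4,2), which is 4 + 2 = 6 occurrences, so a criterion is certain only at the seventh. With *or higher* it is certain at the fifth. Under the cumulative version, moving an event from grade 2 to grade 3 leaves *a* + *b* unchanged and raises *b*, so no upgrade can switch a criterion off. This step needs no assumed rates.

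**Step 2: how often.** A pause acts only on enrolment and on a single Day 1 dose, so the relevant counts are those while subjects remain undosed. Inputs:

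- *n* = 14 and 21 subjects dosed (two and three blocks of seven), with *n* = 28 for reference.
- Per-subject rates *p*₂ and *p*₃ for one AE term. These are assumptions, because the documents give no rates by term and grade.
- At most one event per subject, no SAE, and full AE follow-up of those dosed.

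P(*a*,*b*) = *n*! / (*a*! *b*! (*n*−*a*−*b*)!) × *p*₂^*a* × *p*₃^*b* × (1−*p*₂−*p*₃)^(*n*−*a*−*b*), summed over the three patterns.

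Worked case, *n* = 21, *p*₂ = 0.10, *p*₃ = 0.02:

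- (4,1): 101,745 × 0.10⁴ × 0.02 × 0.88¹⁶ = 0.0263
- (3,2): 203,490 × 0.10³ × 0.02² × 0.88¹⁶ = 0.0105
- (4,2): 813,960 × 0.10⁴ × 0.02² × 0.88¹⁵ = 0.0048
- Sum = 0.0416, or 4.2%

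Chance of being in the gap:

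| Assumed grade 2 / grade 3 rate | n = 14 | n = 21 | n = 28 (nothing left to pause) |
|---|---|---|---|
| 5% / 1% | 0.05% | 0.35% | 1.1% |
| 10% / 2% | 1.0% | 4.2% | 8.6% |
| 10% / 5% | 2.6% | 9.3% | 15.7% |

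The last row is an extreme. It gives a single AE term, at grade 2 or 3, the whole upper end of the 1 to 15% range that Protocol 1.2.2 reports for adverse reactions to immunoglobulin products.

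**Step 3: effect of the rewording.** At 10%/2%, the chance that one AE term meets a criterion goes from 1.2% to 2.1% by subject 14 and from 6.0% to 10.2% by subject 21. The second difference, 10.2 − 6.0 = 4.2 points, is the gap probability, as it should be.

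**Step 4: grade 4.** Two grade 3 events plus one non-serious grade 4 event also meet nothing as written. Few events qualify. Life-threatening events, inpatient admissions and important medical events are SAEs under Protocol 8.1.2 and trigger at one. A temperature above 40.0 °C is grade 4 by value in Protocol Appendix IV without necessarily being an SAE. SAP 9.2.1 is looser ("Potentially Life-Threatening (Grade 4): emergency room visit or hospitalization"), and 8.1.2 excludes outpatient treatment without an overnight stay from SAEs. But the emergency-visit entries in Appendix IV, such as "<85 or ER visit or hospitalization for hypoxia", concern conditions likely to be judged important medical events.

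**The case against.** The strongest reply is that little is lost in practice. Meeting a criterion does not force a pause. Protocol 8.9 and SAP 10.1 separately provide for ongoing SMC review, and under 8.9 the committee may recommend pausing or stopping. The first seven subjects are staggered, and the SMC reviews their available safety data, whatever the grade, before the other 21 are dosed. All of this stands, and it is why the point is minor. It does not make the stated criteria consistent: general review is not the event-specific recommendation promised in 8.11.

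A second reply is that the Charter may already count cumulatively. It may, but 8.11 leaves procedures to the Charter and states the criteria itself. Without the Charter, neither closure nor persistence of the gap can be assumed.

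Three stronger readings are tempting and are not supported.

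- *Grade 4 events never count.* Most would be SAEs and would trigger at one.
- *The gap is large.* If exactly five occurrences of an AE arise and 20% of such occurrences are grade 3, the chance of meeting no criterion is 5(0.2)(0.8)⁴ + 10(0.2)²(0.8)³ = 0.410 + 0.205 = 61.4%. That figure presupposes the cluster and an assumed grade split; it is not the chance of the problem arising.
- *The *n* = 28 probabilities measure the consequence.* By then every subject has been dosed.

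**Conclusion.** The point holds as a minor defect in a stated rule. That the trigger is not monotone, and that the certain trigger moves from the fifth to the seventh occurrence, follow from the literal wording alone. The size depends on assumed rates: for one AE term while subjects remain undosed, 0.05% to 0.35% at 5%/1% and 1.0% to 4.2% at 10%/2%. Full AE follow-up of everyone dosed is also assumed; with incomplete follow-up, fewer events would be known at those points. Non-serious grade 4 events add only a marginal further case. The documents do not show that a safety signal would go unreviewed, only that some mixed-grade clusters lack the listed prompt for an SMC recommendation.

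**What to change.** In Protocol 8.11 and the synopsis, reword the two AE criteria to *three or more of the same AE of grade 3 or higher* and *five or more of the same AE of grade 2 or higher*, and keep the SAE criterion. Match the wording in SAP 2.2 and the SMC Charter. This closes every pattern listed above, including the grade 4 one (2 + 1 = 3), so a separate grade 4 trigger is not needed for consistency. The SMC keeps its discretion over whether to pause.

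The cost is a protocol amendment, which Protocol 12.7 requires the Principal Investigator, the sponsor and the IRB to approve in writing before implementation, so it is best bundled with another change. The operational downside is an occasional extra SMC review, of the size shown in step 3.

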## 9 STATISTICAL CONSIDERATIONS

This section is a summary of the planned statistical analyses. The details are described in the Statistical Analysis Plan (SAP).

Subject disposition will be provided for all who sign and date the ICF.

### 9.1 Sample Size Calculation

There was no formal sample size calculation for this Phase 1 study. However, based on previous experience with hyperimmune globulin products manufactured by Emergent (see Section 1.2.2) in Phase 1 clinical studies with healthy adults, Emergent deems the number of subjects planned to receive study treatments (one of three dose levels of COVID-HIGIV or saline placebo) in the study [N=28; n=8 COVID-HIGIV dosage 1; n=8 COVID-HIGIV dosage 2; n=8 COVID-HIGIV dosage 3, n=4 placebo] is sufficient to descriptively assess COVID-HIGIV safety and PK of a single dose in healthy adults.

### 9.2 Analysis Sets

The following analysis sets will be evaluated in the study:

- Safety Set (SS): all randomized subjects who receive any amount of COVID-HIGIV or placebo, analyzed according to the actual study treatment arm.
- PK Set (PKS): all subjects who are randomized and received COVID-HIGIV according to the protocol and with evaluable PK data (i.e., no major protocol deviations affecting PK sampling and results, adequate number of PK sample test results).

### 9.3 Study Endpoints

#### 9.3.1 Primary Safety Endpoints

The following primary safety endpoints will be evaluated:

- Frequency and severity of AEs within 72 hours post-dosing.
- AEs leading to discontinuation or temporary suspension of infusion.
- AEs and SAEs in healthy adults up to 84 days post-administration of a single dose.

The primary safety endpoints will be evaluated using the following safety assessments over the 84-day follow-up period after administration of a single COVID-HIGIV dose:

- Adverse events.
- Physical exams (complete and/or targeted physical exams).
- Safety laboratory tests (chem 7 panel, total and direct bilirubin, ALT, AST, LDH, CBC with differential, urinalysis).
- Vital signs (oral temperature, seated blood pressure, resting heart rate, pulse oximetry and respiratory rate).

- Concomitant medications.

### 9.3.2 Primary PK Endpoints

The following primary PK endpoints will be evaluated in healthy adults:

- Primary PK Endpoints (at each of the three COVID-HIGIV dose levels):
  - $AUC_{0\text{-last}}$ : area under the concentration-time curve from time 0 to the last quantifiable concentration after dosing.
  - $AUC_{0\text{-inf}}$ :  $AUC_{0\text{-last}}$  plus the additional area extrapolated to infinity after dosing.
  - $AUC_{0\text{-14d}}$  after dosing.
  - $AUC_{0\text{-28d}}$  after dosing.
  - $C_{\max}$ : maximum observed concentration after dosing.
  - $T_{\max}$ : time at which  $C_{\max}$  occurs after dosing.
  - $C_{\min 28d}$ : observed or estimated concentration at 28 days after dosing.
  - $\lambda_z$ : terminal elimination rate constant after dosing.
  - $T_{1/2}$ : apparent terminal elimination half-life after dosing.
  - $CL$ : systemic clearance after dosing.
  - $V_z$ : volume of distribution after dosing.

**Secondary PK Endpoints:** following body weight normalized PK parameters will be estimated as PK parameter divided by subject body weight (kg) at baseline.

- $C_{\max BWN}$ : Body weight normalized  $C_{\max}$
- $C_{\min 28d BWN}$ : Body weight normalized  $C_{\min 28d}$
- $AUC_{0\text{-14d} BWN}$ : Body weight normalized  $AUC_{0\text{-14d}}$
- $AUC_{0\text{-28d} BWN}$ : Body weight normalized  $AUC_{0\text{-28d}}$
- $AUC_{0\text{-last} BWN}$ : Body weight normalized  $AUC_{0\text{-last}}$
- $AUC_{0\text{-inf} BWN}$ : Body weight normalized  $AUC_{0\text{-inf}}$

The PK endpoints will be based on serum concentrations of SARS-CoV-2 binding and neutralizing antibodies after IV administration of a single COVID-HIGIV dose (up to 84 days post-dosing). Serum concentrations of SARS-CoV-2 binding and neutralizing antibodies will be measured by validated immunobinding (IgG) and pseudovirus neutralization PK assays and the results will be used to calculate the primary PK endpoints.

## **9.4 Handling of Missing Data**

When calculating summary statistics, including geometric mean and 95% confidence intervals (CIs) and PK (SARS-CoV-2 binding and/or neutralizing antibody) concentrations below the assay's limit of quantitation (LOQ) and/or detection (LOD) will be imputed as half of LOQ/LOD values. If the lower bounds of the CIs are below lower LOQ (LLOQ), it will be replaced by “<LLOQ” in the output. Unless otherwise specified, no imputation will be made for missing data and complete data analysis will be used. Missing data due to the COVID-19 pandemic will be indicated.

## **9.5 Interim Analyses**

The SMC will perform blinded review of the safety days after the first seven subjects have completed at least 72 hours of safety follow-up.

## **9.6 Planned Method of Analyses**

In general, continuous endpoints will be summarized by descriptive statistics including number of subjects, mean, standard deviation (SD), median, minimum and maximum. Logarithmic transformation will be used when appropriate, coefficient of variation (CV), geometric mean, and geometric CV will also be summarized. Categorical endpoints will be summarized by the total number of subjects, frequencies and percentages. Unless otherwise specified, CIs are two-sided with 95% confidence. Non-compartment method will be used for estimating PK parameters.

### **9.6.1 Subject Disposition, Demographics, Medical History and Study Treatment Exposure**

Subject disposition, including early termination reasons, will be summarized by study treatment for all subjects. Major protocol deviations will be presented for the safety population. Subject demographics, medical history, and study treatment dosing data will be tabulated for the ITT population and the safety population. Study disruption due to the COVID-19 pandemic will be indicated in the listing of subject disposition.

### **9.6.2 Safety Analyses**

All safety analyses will be conducted on the safety population by treatment group..

#### **Adverse Events (AE)/Serious Adverse Events (SAE):**

AE will be coded to system organ class (SOC) and preferred term using the Medical Dictionary for Regulatory Activities (MedDRA), using the most current version at the time of coding. AEs will be defined as events beginning after study treatment administration that were not present prior to study treatment administration or those that were present prior to study treatment administration and subsequently worsened in severity.

- AE within 72 hours post-dosing will be summarized by SOC and preferred term.

- AEs and SAEs within 84 days post-dosing will be summarized in the same manner as described above in the first bullet.
- Discontinuation or temporary suspension of infusion will be summarized by treatment group.

### **Clinical Laboratory Test Results:**

Laboratory test results and change from baseline will be summarized by time point and study treatment. The clinical significance of abnormality will be assessed by the Investigator. Abnormal laboratory results will be graded with severity grade 1 to 4 (grade 1=mild, through grade 4=potentially life-threatening) according to the DAIDS Table for Grading the Severity of Adult and Pediatric Adverse Events (see [Appendix III](#)). For severity not specifically listed in the severity grading criteria, the PI or designee will use the grading criteria for “illness or clinical AE” to assign the AE severity grading.

Values not meeting criteria for severity of at least grade 1 will be considered as grade 0.

Shift table of abnormality (Low, Normal, High) will be provided for selective laboratory parameters by treatment groups and timepoints.

Shift table of severity grade (0, 1-2,  $\geq 3$ ) will be provided for selective laboratory parameters by treatment groups and timepoints.

